### Schedule of Assessments

*Note: A subject needs to visit the clinical site before breakfast for all study visits except the safety follow-up visit.*

Study Visits 	Screening	Treatment Period							Follow-up
	V1	V2	V3	V4	V5	V6	V7	V8	V9
	Screen (Wk -2)	Baseline (Wk 0)	Wk 2	Wk 4	Wk 6	Wk 8	Wk 10	Wk 12	Wk 14
Informed Consent	X								
Inclusion/Exclusion Criteria	X	X							
Demographic (including height)	X								
Medical/Medication History	X								
Physical Examination	X	X		X		X		X	
Vital Signs and Body Weight	X	X	X	X	X	X	X	X	X
12-lead ECG	X							X	
Blood Sampling for serum chemistry, hematology, FPG, HbA1c, hCG, TSH, T3, and T4 	X	X		X		X		X	
Blood Sampling for zinc, insulin, adiponectin, C-peptide, leptin, glucagon, (CHP in a subset of subjects  )		X		X		X		X	
Urine Sampling for glucose, microalbumin, copper, and zinc		X		X		X		X	
Dispense and Review Daily Log	X	X	X	X	X	X	X	X	
Dispense and Review Medications		X	X	X	X	X	X	X	
Waist Circumference		X		X		X		X	
OGTT 		X						X	
ADDQoL Questionnaire		X						X	
Review of Adverse Event and Concomitant Medication 		X	X	X	X	X	X	X	X

- 1) Visits 3 to 8 have ±3 day visit window and Visit 9 has +7 day visit window.
- 2) Serum chemistry, hematology: Weeks -2, 0, 4, 8, and 12  
HbA1c: Weeks -2, 0, 4, 8, and 12  
FPG: Weeks 0, 4, 8, and 12  
TSH, T3, T4: Weeks 0 and 12  
Serum hCG (pregnancy): Weeks -2 and 12
- 3) CHP levels may be analyzed in a subset of subjects if residual serum and/or plasma samples are available after completion of protocol-required tests.
- 4) See Appendix 1.
- 5) Assess hypoglycemic & hyperglycemic episodes at Visits 2 to 8 only.

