If a subject experiences an increase in FPG level of >270 mg/dl from baseline to Week 6 or >240 mg/dl from Week 6 to 12, the subject will be instructed to take his/her own hypoglycemic agent. It is expected that glucose levels can be controlled in most diabetic subjects by these treatments. If the subject's blood glucose levels do not decrease to an acceptable level (<240 mg/dl) after 2 weeks, the subject will be referred to a diabetologist and will be terminated from the study. The study physician will continue to evaluate and treat the subject as needed until healthcare is turned over to the diabetologist.

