#### **Appendix 4: Determining Hypoglycemic and Hyperglycemic Episodes**

For this study, a subject will be described as having hypoglycemic or hyperglycemic episodes when the following definitions are met:

- Documented Symptomatic Hypoglycemia is defined as an event during which typical symptoms of hypoglycemia are accompanied by a measured plasma glucose concentration  $\leq 70$  mg/dl.
- Asymptomatic Hypoglycemia is defined as an event not accompanied by typical symptoms of hypoglycemia but with a measured plasma glucose concentration  $\leq 70$  mg/dl.
- Probable symptomatic hypoglycemia is defined as an event during which symptoms of hypoglycemia are not accompanied by a plasma glucose determination, but that was presumably caused by a plasma glucose concentration  $\leq 70$  mg/dl.
- Relative Hypoglycemia is defined as an event during which the person with diabetes reports of the typical symptoms of hypoglycemia, and interprets those as indicative of hypoglycemia, but with a measured plasma glucose concentration  $> 70$  mg/dl.
- Severe Hypoglycemia is defined as an event requiring assistance of another person to actively administer carbohydrate, glucagons, or other resuscitative actions, or when a measured plasma glucose concentration is  $< 40$  mg/dl.
- Hyperglycemia is defined as plasma glucose level  $> 140$  mg/dl.
- Severe hyperglycemia is defined as plasma glucose level  $> 300$  mg/dl.

\* *Definitions of hypoglycemic episodes were defined per "Defining and Reporting Hypoglycemia: A report from the American Diabetes Association Workgroup on Hypoglycemia" from May, 2005 issue of Diabetes Care.*

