    - (2) Hyperglycemia occurred after previous visit will be summarized with the number of subjects who are occurred episode and the count of episode by each visit separately.
    - (3) Sponsor defined Hypoglycemia (blood glucose  $\leq 70$  mg/dL) occurred after previous visit will be summarized with the number of subjects who are occurred episode and the count of episode by each visit separately.

- (4) Sponsor defined Hyperglycemia (blood glucose  $\geq$  180 mg/dL) occurred after previous visit will be summarized with the number of subjects who are occurred episode and the count of episode by each visit separately.

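### Protocol 9.5 words its only numeric trigger for acting on high glucose as an increase in FPG; read literally it acts only above the protocol's own severe level, so it should be restated as levels

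*Protocol*

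**What the plan says.** Protocol 5.8 sends the handling of hyperglycaemia to Section 9.5. There, action starts on "an increase in FPG level of >270 mg/dl from baseline to Week 6 or >240 mg/dl from Week 6 to 12". At that point "the subject will be instructed to take his/her own hypoglycemic agent". If glucose values then "do not decrease to an acceptable level (<240 mg/dl) after 2 weeks", the subject is referred to a diabetologist and leaves the study. Until handover, "The study physician will continue to evaluate and treat the subject as needed until healthcare is turned over to the diabetologist".

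The other figures for high glucose start no action:
- Appendix 4: "Hyperglycemia is defined as plasma glucose level" above 140 mg/dl, and "Severe hyperglycemia is defined as plasma glucose level" above 300 mg/dl. Both are definitions.
- SAP 10.6.1: "Sponsor defined Hyperglycemia (blood glucose" of at least 180 mg/dL). This is used only to count subjects and episodes.

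The Schedule of Assessments, note 2, gives the laboratory timing as "FPG: Weeks 0, 4, 8, and 12".

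**The concern.** An increase of a stated size, between a start and an end point, is a change and not a level. The next step in the same paragraph is a level of 240 mg/dl. The two steps therefore use different scales, and the text does not say which was intended for the first.

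The rule may well be needed. Protocol 5.8 warns that fasting glucose may rise during roughly the first two months on Cyclo-Z. Protocol 5.9 says diabetes medication doses should stay unchanged during treatment, which gives a site a reason to wait for a stated trigger. Protocol 4.1 foresees two or three sites and SAP 3.1.1 up to four. One site could act at 270 or 240 mg/dl while another waits until the value exceeds the severe level, and both could cite the protocol.

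**Working it through.** The plan gives no derived figure to reproduce. The check is simple arithmetic on the protocol's own numbers, all in mg/dl.

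**Inputs.** Stated increases of 270 (baseline to Week 6) and 240 (Week 6 to 12), and the acceptable level of below 240, from Protocol 9.5. Severe hyperglycaemia above 300 and hypoglycaemia at or below 70, from Appendix 4. Upper end of the fasting control range, 130, from Protocol 9.5. The documents give no baseline FPG, so the reference values of 150 and 240 below are assumptions.

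**Step 1. Literal action level = reference FPG + stated increase.**

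| Reference FPG | First window: acts above | Second window: acts above |
|---|---|---|
| 70 | 70 + 270 = 340 | 70 + 240 = 310 |
| 130 | 130 + 270 = 400 | 130 + 240 = 370 |
| 150 (assumed) | 150 + 270 = 420 | 150 + 240 = 390 |
| 240 (assumed) | 240 + 270 = 510 | 240 + 240 = 480 |

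**Step 2. When is the literal level at or beyond the severe level?** First window: reference at least 300 − 270 = 30. Second window: reference at least 300 − 240 = 60. The only exception in the plausible range is a second-window reference below 60, which Appendix 4 already classes as hypoglycaemia. Put the other way, a rise from 70 to 300 is 230, less than either 240 or 270, so reaching the severe level does not meet the trigger.

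**Step 3. Distance between the two readings.** (reference + 270) − 270 = reference, and likewise for 240. The readings differ by the subject's whole reference FPG, so by more than 70 for everyone who is not hypoglycaemic at the reference point.

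**Step 4. Level reading against the severe level.** 300 − 270 = 30 and 300 − 240 = 60. As levels, the triggers fall 30 and 60 below severe, and the second equals the paragraph's own limit of 240.

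**Step 5. Can the literal rule be computed?** If the second window is a change measured from Week 6, it needs a Week 6 value, and laboratory FPG is taken only at Weeks 0, 4, 8 and 12. It cannot be computed from scheduled laboratory FPG. If the reference is baseline in both windows, Steps 1 to 3 apply unchanged with baseline as the reference.

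**Step 6. Boundary and analyte.** Week 6 belongs to both windows: on the level reading, a Week 6 value of 241 to 270 triggers in the second and not in the first. The trigger names FPG, while the recheck speaks of blood glucose. Two weeks after the Week 4 or Week 8 sample is Week 6 or Week 10, and neither has a scheduled laboratory FPG.

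**The case against.** The strongest reply is that the literal reading is not what anyone meant. The recovery limit in the same paragraph is a level, it equals the second trigger, and the schedule offers no Week 6 laboratory value for a change. A sensible investigator would read levels. This stands as to intent, and it makes the defect a wording error. It does not remove the defect, because the words still say increase and this is a safety threshold that several sites must apply alike.

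A reader might go further and infer that a subject above 300 mg/dl would be left without any required care. The documents do not support that. Protocol 9.5 obliges the investigator to follow ADA standard of care at any glucose level. Protocol 4.3 allows withdrawal on an important laboratory finding, Section 6 allows extra standard-of-care procedures, Section 6.4 allows unscheduled visits, and Section 7.2 allows departures to remove an immediate hazard. What is missing is a uniform number, not a duty to act.

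It is also fair to say that rewording leaves the first action weak: a subject who already takes stable therapy gains little from being told to take it. Whether to allow a step-up in treatment is a separate design choice.

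**Conclusion.** The trigger is wrongly worded and should be corrected. Taken as written, it acts only above 340 or 310 mg/dl for any reference FPG above 70 mg/dl, against a severe level of 300 mg/dl. Taken as levels, it acts above 270 or 240 mg/dl. The literal figures use protocol numbers only and assume that the subject is not hypoglycaemic at the reference point. That levels were intended is an inference from the paragraph and the schedule, though a strong one.

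Two further inferences are not supported. The documents do not show that the sponsor chose to tolerate values above 300 mg/dl. Nor do they give a baseline FPG distribution, so no count of affected subjects can be stated. Home fasting readings are logged daily, and a reader might conclude that they should drive the rule. The text does not establish this, and it would be a substantive change.

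**What to change.** Subject to clinical confirmation of the levels, replace the trigger in Protocol 9.5 with: *If FPG is above 270 mg/dl at any time after baseline and before the Week 6 visit, or above 240 mg/dl at or after the Week 6 visit through Week 12, ...* Use FPG as the analyte for the recheck against 240 mg/dl too. Whether home glucometer values may also trigger the rule is a separate clinical decision for the sponsor and is not part of this change.

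**Cost.** The edit is one paragraph, with no new scheduled visit. If the recheck uses laboratory FPG, a subject who triggers at Week 4 or 8 needs an unscheduled sample at Week 6 or 10, which Protocol 6.4 permits.

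The real cost is in retention. More subjects may meet a level trigger, and those not below 240 mg/dl after two weeks are terminated. They then leave the Per Protocol Set (SAP 7.3) and may have no Week 12 value for the primary analysis, which uses observed data (SAP 9.3.3). With 16 subjects per arm, each such loss is 1/16, or about 6%, of an arm. No entry criterion caps FPG, so a subject stable above 240 mg/dl at entry could be terminated without having worsened. Before fixing the levels, the sponsor should count how many subjects exceed them in blinded, pooled Week 0 FPG, which is already collected.

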## **10. USE OF DATA AND PUBLICATION**

All data and results and all intellectual property rights in the data and results derived from the study will be the property of the Sponsor, who may utilize the data in various ways, such as for submission to government regulatory authorities or disclosure to other investigators. The investigator, while free to utilize data derived from the study for scientific purposes, must discuss any publication with the Sponsor prior to release and obtain written consent of the Sponsor on the intended publication. The Sponsor recognizes the right of the investigator to publish the results upon completion of the study. However, the investigator must send a draft manuscript of the publication or abstract to the Sponsor thirty days in advance of submission in order to obtain approval prior to submission of the final version for publication. This will be reviewed promptly and approval will not be withheld unreasonably. In case of a difference of opinion between the Sponsor and the investigator(s), the contents of the publication will be discussed in order to find a solution that satisfies both parties.

The investigator is encouraged to participate in the evaluation of the data for scientific purposes but is expected to work with the Sponsor in the development of any scientific presentation or publication. Since the Sponsor authors will be included, it is expected that all co-authors of the manuscripts will have an opportunity for feedback in the content and conclusions. The technical and editorial resources of the Sponsor will be available to assist in the development of abstracts, presentations, and publications regarding this study, and it is expected that drafts will be sent to the Sponsor with adequate time for input and revisions prior to submission.

## **12. APPENDICES**

### **Appendix 1: Oral Glucose Tolerance Test (OGTT)**

Subjects will be advised to maintain similar exercise and eating habits 3 days prior to the OGTT. Each subject will be instructed not to take his or her usual oral medications or insulin injection and food at least 12 hours before coming to the clinical site between 7:00 am and 8:30 am for an OGTT. Each subject will be allowed to drink only water during the 12-hour fasting period prior to the OGTT and advised not to consume any food. Initial blood will be drawn (15 min prior to OGTT) for serum chemical analysis. The subject will then consume a glucose solution (75 g), followed by one drop of blood drawn for glucose measurements with a glucometer at 0, 0.5, 1.0, 1.5, 2.0, 2.5 and 3 h in the clinical site.

**Appendix 2: Daily Log**

**Subject Diary**

A Multicenter, Randomized, Double-blind, Placebo-controlled, Phase 2 Study to Evaluate the Efficacy and Safety of Cyclo-Z in Patients with Obese Type 2 Diabetes

Protocol No.	NMP-CYZ-P2-001						
Subject Initial	
 
 				
 
						
Screening No.	
 
 	-			
 
				-		
	-						
	Code*		Number				

\* Site Number

**< How to fill out this diary >**

- Please record this diary everyday starting the evening of the day it's dispensed until the morning of your next visit to the hospital.
- Return this diary to the person in charge of this study at your next visit. You will receive a new diary at each visit.
- Study Site: This is the name of the hospital you will be visiting for the study.
- Date Dispensed: This is the date you received this diary. Please record it in the format of DD/MMM/YYYY (Example: 03 Feb 2015).
- Date: This is the date you checked your blood sugar levels and took the study medication. Please record it in the format of DD/MMM/YYYY (Example: 03 Feb 2015).
- Blood Sugar: Please check the unit in which your blood sugar level is measured.
- Fasting before breakfast: Write down your blood sugar level tested in a fasted state before breakfast.
- 2 hours after dinner: Write down your blood sugar level tested 2 hours after dinner.
- Not done: If you did not check your blood sugar, please check the box and state the reason.
- Study Medication: Please check whether you took the study medication or not. On the evening before your visit to the hospital, indicate when you took study medication in a 24 hour format (Example: 6:00 pm = 18:00, 8:00 pm = 20:00).
- Not taken: If you did not take your study medication, please check the box and state the reason.
- If you are unable to return to the study site 14 days after your previous visit, use the additional rows provided to continue recording your blood sugar levels and the study medication compliance until your next visit.
- Comments: Please leave any comments, questions or concerns you may have. Also inform the study staff of any changes to your diet or exercise regimen.
- Diary return date and confirmation signature: Please record the date the diary is returned to the site and your signature to confirm.

*If you have any further questions or problems about filling out the diary or the study in general, please contact your clinical site.*

Date Dispensed		(Example: 03 Feb 2015)	
Day	Date (DD/MMM/YYYY)	Blood Sugar (  mg/dl  mmol/L)	
1		Fasting before breakfast	2 hours after dinner
		N/A	
		 Not done (reason: )	
Study Medication:  Taken  Not taken (reason: )			
2		Fasting before breakfast	2 hours after dinner
		 Not done (reason: )	
		Study Medication:  Taken  Not taken (reason: )	
3		Fasting before breakfast	2 hours after dinner
		 Not done (reason: )	
		Study Medication:  Taken  Not taken (reason: )	
4		Fasting before breakfast	2 hours after dinner
		 Not done (reason: )	
		Study Medication:  Taken  Not taken (reason: )	
5		Fasting before breakfast	2 hours after dinner
		 Not done (reason: )	
		Study Medication:  Taken  Not taken (reason: )	
6		Fasting before breakfast	2 hours after dinner
		 Not done (reason: )	
		Study Medication:  Taken  Not taken (reason: )	
7		Fasting before breakfast	2 hours after dinner
		 Not done (reason: )	
		Study Medication:  Taken  Not taken (reason: )	
8		Fasting before breakfast	2 hours after dinner
		 Not done (reason: )	
		Study Medication:  Taken  Not taken (reason: )	
9		Fasting before breakfast	2 hours after dinner
		 Not done (reason: )	
		Study Medication:  Taken  Not taken (reason: )	
10		Fasting before breakfast	2 hours after dinner
		 Not done (reason: )	
		Study Medication:  Taken  Not taken (reason: )	
11		Fasting before breakfast	2 hours after dinner
		 Not done (reason: )	
		Study Medication:  Taken  Not taken (reason: )	

12		Fasting before breakfast	2 hours after dinner
		□Not done (reason: )	
		Study Medication: □Taken □Not taken (reason: )	
13		Fasting before breakfast	2 hours after dinner
		□Not done (reason: )	
		Study Medication: □Taken □Not taken (reason: )	
14		Fasting before breakfast	2 hours after dinner
		□Not done (reason: )	
		Study Medication: □Taken □Not taken (reason: )	
()		Fasting before breakfast	2 hours after dinner
		□Not done (reason: )	
		Study Medication: □Taken □Not taken (reason: )	
()		Fasting before breakfast	2 hours after dinner
		□Not done (reason: )	
		Study Medication: □Taken □Not taken (reason: )	
()		Fasting before breakfast	2 hours after dinner
		□Not done (reason: )	
		Study Medication: □Taken □Not taken (reason: )	
()		Fasting before breakfast	2 hours after dinner
		□Not done (reason: )	
		Study Medication: □Taken □Not taken (reason: )	
()		Fasting before breakfast	2 hours after dinner
		□Not done (reason: )	
		Study Medication: □Taken □Not taken (reason: )	
Time you took your medication the evening before your visit to hospital:			
Comments			
Please leave any comments, questions or concerns you may have. Also inform the study staff of any changes to your diet or exercise regimen.			

Please fill out the following when you return the diary at each visit.

Diary Return Date (DD/MMM/YYYY)	
Subject Signature	
Reviewer Signature	

### Appendix 3: Audit of Diabetes-Dependent Quality of Life (ADDQoL) Questionnaire

## ADDQoL

This questionnaire asks about your quality of life – in other words how good or bad you feel your life is.

Please put an "X" in the box that best indicates your response for each item.

What we want to know is how you feel about your life now.

I) In general, my present quality of life is:						
						
excellent	very good	good	neither good nor bad	bad	very bad	extremely bad

Now we would like to know how your quality of life is affected by your diabetes, its management and any complications you may have.

II) If I did not have diabetes, my quality of life would be:				
				
very much better	much better	a little better	the same	worse

Please respond to the more specific items on the pages that follow. For each aspect of life described, you will find two parts:

For Part (a): put an "X" in one box to show how diabetes affects this aspect of your life;  
For Part (b): put an "X" in one box to show how important this aspect of your life is to your quality of life.

1	(a)	If I did not have diabetes, I would enjoy my leisure activities:  very much more  much more  a little more  the same  less
	(b)	My leisure activities are:  very important  important  somewhat important  not at all important

2	Are you currently working, looking for work or would like to work? Yes  If yes, complete (a) and (b). No  If no, go straight to Question 3.
	(a) If I did not have diabetes, my work life would be:  very much better  much better  a little better  the same  worse
	(b) For me, having a work life is:  very important  important  somewhat important  not at all important

3	(a)	If I did not have diabetes, local or long distance travel would be:  very much easier  much easier  a little easier  the same  more difficult
	(b)	For me, local or long distance travel are:  very important  important  somewhat important  not at all important

4	
Do you ever go on vacation or want to go on vacation?                  Yes  If yes, complete (a) and (b).                  No  If no, go straight to Question 5.

(a)	
If I did not have diabetes, my vacations would be:
 
                                                                                                           very much better    much better    a little better    the same    worse             

(b)	
For me, vacations are:
 
                                                                                     very important    important    somewhat important    not at all important             

5 (a)	
If I did not have diabetes, physically I could do:
 
                                                                                                           very much more    much more    a little more    the same    less             

(b)	
For me, how much I can do physically is:
 
                                                                                     very important    important    somewhat important    not at all important             

6	
Do you have any family/relatives?                  Yes  If yes, complete (a) and (b).                  No  If no, go straight to Question 7.

(a)	
If I did not have diabetes, my family life would be
 
                                                                                                           very much better    much better    a little better    the same    worse             

(b)	
My family life is:
 
                                                                                     very important    important    somewhat important    not at all important             

7 (a)	
If I did not have diabetes, my friendships and social life would be:
 
                                                                                                           very much better    much better    a little better    the same    worse             

(b)	
My friendships and social life are:
 
                                                                                     very important    important    somewhat important    not at all important             

8	
Do you have or would you like to have a close personal relationship (e.g. husband / wife, partner)?
 
Yes  If yes, complete (a) and (b).
 
No  If no, go straight to Question 9.

(a)	
If I did not have diabetes, my closest personal relationship would be:
 
                                                                                          
 
                 very much better      much better      a little better      the same      worse             

(b)	
For me, having a close personal relationship is:
 
                                                                    
 
                 very important      important      somewhat important      not at all important             

9	
Do you have or would you like to have a sex life?
 
Yes  If yes, complete (a) and (b).
 
No  If no, go straight to Question 10.

(a)	
If I did not have diabetes, my sex life would be:
 
                                                                                          
 
                 very much better      much better      a little better      the same      worse             

(b)	
For me, having a sex life is:
 
                                                                    
 
                 very important      important      somewhat important      not at all important             

10 (a)	
If I did not have diabetes, my physical appearance would be:
 
                                                                                          
 
                 very much better      much better      a little better      the same      worse             

(b)	
My physical appearance is:
 
                                                                    
 
                 very important      important      somewhat important      not at all important             

11 (a)	
If I did not have diabetes, my self-confidence would be:
 
                                                                                          
 
                 very much better      much better      a little better      the same      worse             

(b)	
My self-confidence is:
 
                                                                    
 
                 very important      important      somewhat important      not at all important             

12 (a)	If I did not have diabetes, my motivation would be:					
		very much better	much better	a little better	the same	worse
(b)	My motivation is:					
		very important	important	somewhat important	not at all important	

13 (a)	If I did not have diabetes, the way people in general react to me would be:					
		very much better	much better	a little better	the same	worse
(b)	The way people in general react to me is:					
		very important	important	somewhat important	not at all important	

14 (a)	If I did not have diabetes, my feelings about the future (e.g. worries, hopes) would be:					
		very much better	much better	a little better	the same	worse
(b)	My feelings about the future are:					
		very important	important	somewhat important	not at all important	

15 (a)	If I did not have diabetes, my financial situation would be:					
		very much better	much better	a little better	the same	worse
(b)	My financial situation is:					
		very important	important	somewhat important	not at all important	

16 (a)	If I did not have diabetes, my living situation and conditions would be:					
		very much better	much better	a little better	the same	worse
(b)	My living situation and conditions are:					
		very important	important	somewhat important	not at all important	

17 (a)	If I did not have diabetes, I would have to depend on others when I do not want to:			
				
very much less	much less	a little less	the same	more
(b)	For me, not having to depend on others is:			
				
very important	important	somewhat important	not at all important	

18 (a)	If I did not have diabetes, my freedom to eat as I want would be:			
				
very much greater	much greater	a little greater	the same	less
(b)	My freedom to eat as I want is:			
				
very important	important	somewhat important	not at all important	

19 (a)	If I did not have diabetes, my freedom to drink as I want (e.g. fruit juice, alcohol, sweetened hot and cold drinks) would be:			
				
very much greater	much greater	a little greater	the same	less
(b)	My freedom to drink as I want is:			
				
very important	important	somewhat important	not at all important	

Are there any other ways in which diabetes, its management and any complications affect your quality of life? If so, please write what they are below.

For information only
----------------------

Thank you for completing this questionnaire.

